4.0 Treatment plan

4.1 Overview

This will be a phase II, non-randomized trial to determine the efficacy and safety of the combination of Eribulin, and lenvatinib in patients with metastatic breast cancer, non-small cell lung cancer and sarcoma. Treatments will be given in cycles of 3 weeks (21 days) and staging scans(CT Scans) will be performed every 2 cycles. Bone scans and MRI brain will be optional. Toxicity assessment will take place after each cycle.

Eribulin will be administered on cycle days 1 and 8; lenvatinib is an orally administered medication which will be given daily throughout each cycle (on cycle 1 lenvatinib will be started on day 2). On days when both drugs are administered, Eribulin will be administered immediately prior to lenvatinib.

Patients will be followed after treatment discontinuation until disease recurrence or death. An evaluable patient for toxicity is any patient who has received at least 1 dose of any of the study drugs. An evaluable patient for efficacy is any patient who has received at least 2 cycles of therapy.

There will be a safety run-in phase. Ten patients will receive lenvatinib at 20 mg daily and Eribulin at 1.4 mg/m² day 1 and day 8 of a 21 day cycle. Eribulin will be given on day 1 and lenvatinib at 20 mg daily will be started on day 2. After completion of 1 cycle of therapy for the first 10 patients the PI will have a teleconference with the medical team at EISAI and decide whether to continue at the same dose or increase the dose to 24 mg daily of lenvatinib and Eribulin at 1.4 mg/m² day 1 and day 8 of a 21 day cycle.

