4.2 Study Drug Administration

Eribulin

Eribulin will be administered intravenously (IV) on days 1 and 8 of each cycle at a dose of 1.4 mg/m² over a 2-5 minute time period; on cycle day 1 in the Phase II portion of the trial; this will be immediately prior to Lenvatinib administration. Eribulin will be administered to the patient in the clinic (for drug preparation instructions, see section 7.0). Each cycle will last 21 (+/- 3) days. Laboratory tests will be performed within 2 days prior to days 1 and 8 of all cycles to assess toxicity and confirm that it is safe to proceed with treatment (see Section 7.0 for a complete listing of assessments). The dose of Eribulin will be calculated based on the BSA at study entry and *should only be recalculated if there is >10% change in body weight from baseline*. The actual body weight will be used for these calculations.

Lenvatinib

Lenvatinib will be self-administered by patients orally once a day during the study period. Patients will self-administer lenvatinib at home, except on study visit days. On these visit days, patients should take lenvatinib after chemotherapy is administered. Patients will be instructed to take each dose orally once daily, with or without food, starting on day 2 of cycle 1. The capsules should be swallowed whole without chewing, dissolving, or opening them. Patients should be instructed to take their dose of study drug at the same time each day. If the usual dosing time is missed, the patient should take the dose that day as soon as they remember as long as this is within 12 hours of the usual time the patient takes the dose. If it has been over 12 hours then this will be considered a missed dose. Patients should not make up missed or vomited doses; dosing should resume on the next calendar day unless otherwise instructed. Patients will be given a medication diary to record all doses taken, missed/skipped, or vomited. This diary will be reviewed with study personnel prior to dispensing medication for the next cycle.

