4.3 Supportive Care Guidelines

Supportive therapy for neutropenia:

If grade 3 or 4 neutropenia develops (ANC<1000/uL), G-CSF (Neupogen) can be administered, at the discretion of the treating investigator, until resolution of neutropenia. Neulasta (PEG-filgrastim) 6mg SC for 1 dose is recommended. If Neulasta is given, chemotherapy cannot be administered within 14 days. Neupogen can also be given at the discretion of the treating investigator. NOTE: Neupogen can be given any time before or after chemo. HOWEVER, Neulasta cannot be given within 14 days of chemotherapy.

Supportive therapy for neuropathy

Gabapentin or similar medications can be given at the discretion of the treating physician per institutional practice.

Dose Delays & Dose Modifications

Toxicities will be graded using NCI CTCAE version 4.03 (see Appendices). Dose delays and modification of lenvatinib and Eribulin are summarized below (for post-DLT period in phase II patients only). Individual patient dose reductions are also provided in separate tables.

Dose Delay & Modification for Eribulin and Lenvatinib

Toxicity	Adverse event	Dose Reduction/Delay	
		Eribulin	Lenvatinib
Hematologic toxicity attributed to any or all treatment	Platelets 75000-99999/mm ³ within 24 hrs prior to scheduled therapy	If Day 1: Hold until recovery of platelets >100,000/mm ³ . Resume at the same level after recovery If Day 8: No intervention	No dose modification necessary
	ANC <1000/mm ³ or Platelets 25000-74999/mm ³ within 24 hrs prior to scheduled therapy	If Day 1: Hold until recovery to ANC >1000/mm ³ and Platelets 100000/mm ³ . Resume at same level after recovery If Day 8: Hold until recovery to ANC >1000/mm ³ and Platelets 75000/mm ³ . Resume at same level after recovery	Hold until recovery to ANC >500/mm ³ and platelets more than 25000, Resume at same level after recovery.
	Platelets <25000/mm ³ or Platelets 25000-50000/mm ³ complicated by bleeding, easy bruising, petechiae, or requiring platelet transfusion	If Day 1: Hold until recovery to Platelets 100000/mm ³ . Resume at same level after recovery If Day 8: Hold until recovery to Platelets 75000/mm ³ . Resume at same level after recovery	Hold until recovery of Platelets 25000/mm ³ . Resume at current dose level.

	Prolonged neutropenia (ANC<500/mm ³ for >7 days)	Hold until recovery to ANC>1000/mm ³ . Resume at one dose level below current dose level	Hold until recovery to ANC>500/mm ³ . Resume at same level dose.

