Proteinuria	>2 gms or less than 2 gms	No dose modification necessary.	Withhold lenvatinib for \leq 2 grams of proteinuria/24 hours. Resume at next dose level below current dose level; 2) when proteinuria is >2 gm/24 hours. Discontinue lenvatinib for nephrotic syndrome.
QTc Prolongation	Grade 3 or greater	No dose modification necessary	Monitor and correct electrolyte abnormalities in all patients. Withhold lenvatinib for the development of Grade 3 or greater QT interval prolongation. Resume lenvatinib at a one dose level below previous dose level when QT prolongation resolves to Grade 0 or 1 or baseline.

Day 8 dose of Eribulin may be delayed for a maximum of 1 week. If toxicities do not improve enough after 1 week delay then omit day 8 dose of Eribulin. If day 8 of Eribulin is omitted two consecutive cycles Eribulin should be resumed at one dose below current dose level.

Eribulin Dose Modifications

Starting dose and dose modifications for unacceptable toxicity that is thought to be related to Eribulin are listed below. Dose adjustments are to be made according to the greatest degree of toxicity. The most common toxic effects of Eribulin are fatigue, neutropenia (including neutropenic fever), peripheral neuropathy, and alopecia.

Eribulin Dose Modifications, TABLE 1

0	1.4
-1	1.1
-2	0.7

NOTE: Patients requiring a third dose reduction should be taken off study unless in the opinion of the investigator and/or the DSMB there is reason to believe that the patient is still experiencing clinical benefit (in such cases the DSMB will issue written approval).

Lenvatinib Dose Modifications

Recommended Dose Modifications for Persistent and Intolerable Grade 2 or Grade 3 Adverse Reactions or Grade 4 Laboratory Abnormalities, TABLE 2

0	20
-1	14
Note: Based on toxicity data of 1st 10 patients in Phase 2, starting Lenvatinib dose was not increased to 24 mg daily	

Other Toxicities with Lenvatinib

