4.7 Duration of Therapy

Patients may continue on study therapy until disease progression or until unacceptable toxicity occurs.

Patients will go off study therapy if any of the following occurs:

- The patient experiences any grade 4 toxicity after 2 dose modifications, as recommended by the protocol. If treatment is held for 2 consecutive treatment cycles due to toxicity, the patient must go off treatment.
- The patient withdraws consent from treatment or from the study as a whole.
- There is disease progression.
- The treating physician feels it is necessary (e.g. due to patient non-compliance or other safety concerns).

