5.3.4 Endpoint Assessment

The overall response rate (ORR) will be defined as response after scans assessed after two cycles of therapy (1 cycle = 3 weeks). Clinical response will be assessed by the treating physician as outlined above. All patients who are on study after 2 cycles will be considered evaluable for the response endpoints.

Progression-free survival (PFS) will be defined as the time from the first study treatment to the first occurrence of progression or death. All patients who receive at least one dose of each drug will be evaluable for this endpoint.

Toxicity will be assessed NCI CTCAE v 4.03. The incidence, nature, and severity of adverse events will be determined. All patients who receive at least one dose of study drug will be considered evaluable for toxicity and safety endpoints.

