6.0 Study Parameters

Procedures	Screening & Baseline	Cycle 1	Every cycle ²	Every 2 cycles or at study termination	End of study visit ⁷	Follow-Up ⁶
Tissue procurement ¹	X			X ⁵		
Informed consent	X					
Eribulin administration			X (Days 1 & 8)			
Lenvatinib			X once daily (starting on day 2 of cycle 1)			
Medical history ³	X		X		X	
Physical exam ³	X		X		X	
CBC w/ diff	X ³		X		X	
Comprehensive chemistry panel	X ³		X			
TSH	X		X			
Serum pregnancy test	X					
EKG	X		X ¹⁰			
Blood draw for micro RNA assay ⁹		X			X	

Procedures	Screening & Baseline	Cycle 1	Every cycle ²	Every 2 cycles or at study termination	End of study visit ⁷	Follow-Up ⁶
Urine analysis ¹¹	X			X		
Imaging ⁸	X ⁴			X		
Toxicity assessment			X			
Biopsy				X ⁵		
Survival status						X

¹Archival tissue or a fresh biopsy will be required to procure tissue for study purposes. Biopsy does not need to be repeated for study purposes if archived tissue is available.

Tissue procurement is voluntary

²A cycle is defined as 3 weeks or 21 days (+/- 3 days). Eribulin will be given on cycle days 1 and 8 and lenvatinib starting on day 2 of cycle one and then continuously.

³Pre-study laboratory tests, medical history, and physical exam (including performance status and review of systems) must be completed within 28 days prior to registration.

Pre-study CBC and CCP will be repeated on day 1 prior to treatment administration.

⁴Pre-study imaging must be performed within 28 days prior to registration.

⁵At the initiation and completion of study treatment (or at the time of early withdrawal), tissue samples should be obtained for correlative studies. This is voluntary and will only be done on patients who consent to it.

⁶Patients will be followed every 6 months, at the time of routine clinic visit or via phone, until death, to document disease progression and survival.

⁷Within 30 days of last dose of study medications.

⁸Imaging modality is left to the discretion of the investigator. However the same imaging modality should be used every two cycles to assess disease status.

⁹Blood samples for microRNA assay will be collected on Cycle 1, Day 1 and at the end of treatment.

¹⁰Repeat EKG with every cycle in patients with congestive heart failure, bradyarrhythmias, or those who are taking drugs known to prolong the QT interval, including Class Ia and III antiarrhythmics.

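### On-treatment scans are scheduled by cycle count with no calendar anchor, so day 1 eribulin holds can delay scans and, on average, modestly lengthen apparent PFS

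*Combined protocol and SAP*

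**What the plan says.** Every statement of the imaging schedule counts cycles. The Synopsis places imaging after each pair of cycles. Section 4.1 says "staging scans(CT Scans) will be performed every 2 cycles", and footnote 8 to the Section 6.0 table says "the same imaging modality should be used every two cycles to assess disease status". None of them gives weeks from first dose or a scan window.

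On cycle length, Section 4.2 says "Each cycle will last 21 (+/- 3) days", and footnote 2 in 6.0 agrees.

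On holds, the first row of the 4.3 table reads "If Day 1: Hold until recovery of platelets", and other rows also wait for recovery with no maximum in days. For day 8 the rule differs: "Day 8 dose of Eribulin may be delayed for a maximum of 1 week", after which the dose is omitted. The outer limit is in 4.7: "If treatment is held for 2 consecutive treatment cycles due to toxicity, the patient must go off treatment".

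On the endpoint, 5.3.4 states: "Progression-free survival (PFS) will be defined as the time from the first study treatment to the first occurrence of progression or death". It has no rule for late or missed scans. The same section ties the overall response rate (ORR) to scans after two cycles.

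**The concern.** PFS is measured in calendar time, but the imaging that mostly determines it follows treatment cycles. If a day 1 hold postpones a cycle, it also postpones the scan that follows, and progression in the meantime is recorded later. The delay depends on toxicity, so the measurement schedule is not independent of treatment.

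Defining PFS is a named secondary objective. With a single arm, no control group carries the same artefact, so the estimate can be read only against outside figures, which may rest on a different schedule. The scan used for ORR in 5.3.4 has the same timing dependence, so patients could be assessed for response at different calendar times.

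**Working it through.** **The plan's own figure.** Section 8.1.2 has N = 30 and rejects at 10 or more responders. The exact binomial gives P(X >= 10 | p = 0.2) = 0.0611 and P(X >= 10 | p = 0.4) = 0.8237, as stated. Scan timing does not enter this calculation. The plan states no PFS target or power.

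**Does a hold move the scan?** The text points both ways.
- For: day 1 is held until recovery, whereas day 8 is capped at a week and then skipped. Sections 4.1 and 5.3 count cycles received or completed. Section 4.3 bars chemotherapy for 14 days after pegfilgrastim. If it is given after cycle day 11, the next day 1 falls after day 11 + 14 = 25, which is beyond a 24-day cycle.
- Against: a cycle is 21 (+/- 3) days, so two cycles are 36 to 48 days. The 4.7 wording on two consecutive held cycles can be read as cycles elapsing while drug is held.

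Postponement is the better reading, but it is not explicit.

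**Size if holds do move the scan.** The assumptions, which are not in the plan, are exponential progression times, progression found only at scans, and holds unrelated to tumour biology. The median of 3.7 months is the eribulin figure in Section 1.2 and serves as an illustration. It equals 3.7 x 30.44 / 7 = 16.09 weeks, so 1/λ = 16.09 / ln 2 = 23.21 weeks.

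*Every interval of length d.* Mean recorded time = d / (1 - exp(-λd)). The lag is that minus 1/λ.

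| d (weeks) | Mean recorded time | Mean lag | Shift from 6-weekly |
|---|---|---|---|
| 6 | 26.34 | 3.13 | 0 |
| 8 | 27.44 | 4.23 | 1.10 |
| 9 | 28.00 | 4.79 | 1.66 |
| 12 | 29.73 | 6.51 | 3.39 |

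*One hold of k weeks in the first interval, 6-weekly afterwards.* Mean recorded time = (6 + k) + exp(-λ(6 + k)) x 26.34. For k = 2 this is 8 + 0.7085 x 26.34 = 26.66, a shift of 0.32 weeks. The last column comes from simulation.

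| Hold | Mean shift (weeks) | Held patients dated earlier |
|---|---|---|
| 7 days | 0.14 | 14% |
| 14 days | 0.32 | 28% |
| 21 days | 0.53 | 41% |
| 41 days | 1.32 | 76% |

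Some patients are dated earlier because a hold moves the whole later scan grid. At 41 days the grid moves by one day less than a full 42-day interval, so most are dated one day earlier while the rest are dated much later.

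*Sensitivity.* True medians of 5.4 months (the endometrial phase II trial in 2.2) and 2.2 months (the comparator arm in 1.2) give single-hold shifts of 0.7 to 1.6 days for a 7-day hold and 6.6 to 14.4 days for a 41-day hold.

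*Median.* At 3.7 months the observed median is 18 weeks with 6-weekly scans, 24 with 8-weekly and 18 with 9-weekly. At 3.65 months, 8-weekly scans give 16 weeks. The jump to 24 occurs only because 16.09 weeks falls just past the week 16 scan: P(T <= 16) = 0.498.

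**The case against.** Much of the case on the other side stands.

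- The plan does not say that a hold stops the cycle clock. If cycles elapse during a hold, scans stay within 36 to 48 days. This makes the mechanism conditional, but sites could still schedule scans differently.
- Scans are not the only route to an event. Section 5.0 uses physical examination as well as imaging, 6.0 schedules an examination every cycle, and death counts. The shifts above are therefore somewhat too large, although 5.2 prefers imaging when both methods have been used.
- A reader might infer that the bias falls exactly on the patients who tolerate the combination worst. The text does not support that. Lenvatinib-only holds and omitted day 8 doses are not said to move a cycle, and patients who stop because of toxicity have imaging scheduled at study termination. The affected group is patients with day 1 eribulin holds who stay on treatment.
- A reader might take the grade 3/4 neutropenia rates of 54% and 64% in the eribulin risk section as hold rates. They are toxicity incidences. The 4.3 trigger is a count within 24 hours before a scheduled dose, growth factor is permitted, and the plan gives no day 1 delay rate.
- A reader might quote an 18-to-24-week change in median PFS. That is an artefact of the scan grid.
- PFS carries no hypothesis test. That limits the consequence but does not remove the problem, because describing PFS is the stated objective.

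**Conclusion.** The point holds in a limited form. On-treatment imaging has no calendar anchor, and open-ended day 1 holds can delay it. On the better reading of the text, progression in patients with such holds is on average dated later. Under the stated assumptions, one hold costs about 0.1 to 1.3 weeks in the mean, and stretching every interval to 8 weeks costs about 1.1 weeks. The 3.4-week figure requires every interval to reach 12 weeks and is an upper bound. No direction can be claimed for the median. These are shifts in held patients; the shift over all patients is smaller in proportion to how many are held, and the plan does not give that fraction.

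No stated error rate or power is affected. The consequence is for reading a descriptive, single-arm PFS estimate against outside data. It merits correction because the remedy is cheap.

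**What to change.** 1. In the Synopsis, 4.1 and 6.0, schedule imaging every 6 weeks (+/- 7 days) counted from cycle 1 day 1, regardless of dose delays or omitted doses, until progression or end of treatment. The first window, days 35 to 49, contains the 36 to 48 days that two unheld cycles can take.
2. Reconcile the 21 (+/- 3) day cycle in 4.2 and 6.0 with the hold rules in 4.3 and 4.7, so that the text says whether a hold extends the cycle.
3. Do not redefine the 5.3.4 response scan as week 6 alone. Section 4.1 requires at least two cycles received for efficacy evaluability, and 5.3 requires two complete cycles before stable disease is assigned. A fixed week 6 scan could assess held patients too early and create a new conflict in the primary endpoint. One workable rule is the first calendar scan on or after completion of two cycles.

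The cost is protocol wording, an occasional extra scan, and scans that do not always coincide with a day 1 visit. Under the rule in item 3, a patient whose second cycle ends after the week 6 window would have the response scan at week 12. The calendar stops at end of treatment, so it does not address how progression is dated after that.

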Gastrointestinal: Most common are nausea and constipation (occurring in $\geq 25\%$ of patients). Other GI adverse events include diarrhea and vomiting.

Neurologic: Peripheral neuropathy (incidence of $\geq 25\%$) is the most common.

Other: Asthenia/fatigue and alopecia are the most common (occurring in $\geq 25\%$ of patients) miscellaneous adverse events.

Nursing Implications

Monitor CBC and platelet counts.

Monitor for signs of neuropathy.

Monitor for prolonged QT intervals in patients with congestive heart failure, bradyarrhythmias, drugs known to prolong the QT interval, and electrolyte abnormalities.

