7.2 Lenvatinib

Other names

Lenvima

Classification

LENVIMA, a kinase inhibitor, is the mesylate salt of lenvatinib. Its chemical name is 4-[3-chloro-4-(*N*¹-cyclopropylureido)phenoxy]-7-methoxyquinoline-6-carboxamidemethanesulfonate.

Mode of action

Lenvatinib is a receptor tyrosine kinase (RTK) inhibitor that inhibits the kinase activities of vascular endothelial growth factor (VEGF) receptors VEGFR1 (FLT1), VEGFR2 (KDR), and VEGFR3 (FLT4). Lenvatinib also inhibits other RTKs that have been implicated in pathogenic angiogenesis, tumor growth, and cancer progression in addition to their normal cellular functions, including fibroblast growth factor (FGF) receptors FGFR1, 2, 3, and 4; the platelet derived growth factor receptor alpha (PDGFR α), KIT, and RET.

Storage and Stability

Store at 25°C (77°F); excursions permitted to 15–30°C (59–86°F)

Protocol dose

Lenvatinib is administered at a dose of 20 mg orally.

Preparation

LENVIMA 4 mg capsules are supplied as hard hyperomellose capsules with yellowish-red body and yellowish-red cap, marked in black ink with “€” on the cap and “LENV 4 mg” on the body.

LENVIMA 10 mg capsules are supplied as hard hyperomellose capsules with yellow body and yellowish-red cap, marked in black ink with “€” on the cap and “LENV 10 mg” on the body.

Protocol administration

Lenvatinib is administered orally 20 mg po daily. It will be administered immediately after the Eribulin administration.

Incompatibilities

None

Availability

Lenvima will be supplied by Eisai, Inc in cards containing 10 mg and 4 mg capsules. To order drug, please contact EISAI IIS Department at [contact] or [contact]

Side effects

Detailed information regarding side effects and rates of adverse events of lenvatinib can be found in the package insert. Some of the most common side effects include:

Hypertension

The median time to onset of new or worsening hypertension was 16 days for LENVIMA-treated patients. The incidence of Grade 3 hypertension was 44% as compared to 4% for placebo, and the incidence of Grade 4 hypertension was less than 1% in LENVIMA-treated patients and none in the placebo group.

Cardiac dysfunction

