5 WARNINGS AND PRECAUTIONS

5.1 Hypertension

In Study 1 hypertension was reported in 73% of LENVIMA-treated patients and 16% of patients in the placebo group [*see Adverse Reactions (6.1)*]. The median time to onset of new or worsening hypertension was 16 days for LENVIMA-treated patients. The incidence of Grade 3 hypertension was 44% as compared to 4% for placebo, and the incidence of Grade 4 hypertension was less than 1% in LENVIMA-treated patients and none in the placebo group.

Control blood pressure prior to treatment with LENVIMA. Monitor blood pressure after 1 week, then every 2 weeks for the first 2 months, and then at least monthly thereafter during treatment with LENVIMA. Withhold LENVIMA for Grade 3 hypertension despite optimal antihypertensive therapy; resume at a reduced dose when hypertension is controlled at less than or equal to Grade 2. Discontinue LENVIMA for life-threatening hypertension [*see Dosage and Administration (2.2)*].

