5.8 QT Interval Prolongation

In Study 1, QT/QTC interval prolongation was reported in 9% of LENVIMA-treated patients and 2% of patients in the placebo group. The incidence of QT interval prolongation of Grade 3 or greater was 2% in LENVIMA-treated patients compared to no reports in the placebo group. Monitor electrocardiograms in patients with congenital long QT syndrome, congestive heart failure, bradyarrhythmias, or those who are taking drugs known to prolong the QT interval, including Class Ia and III antiarrhythmics.

Monitor and correct electrolyte abnormalities in all patients. Withhold LENVIMA for the development of Grade 3 or greater QT interval prolongation. Resume LENVIMA at a reduced dose when QT prolongation resolves to Grade 0 or 1 or baseline [*see Dosage and Administration (2.2), Clinical Pharmacology (12.2)*].

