DLT evaluation will occur weekly for the first cycle (1 cycle = 21 days).

Any enrolled and treated patient should be evaluated for DLT purposes.

The DLT period as a whole will be the first cycle of treatment. (Adverse events, however, will continue to be collected for the duration of treatment).

In general, a non-hematologic DLT is defined as any Grade ≥ 3 toxicity, and a hematologic DLT is defined as any Grade ≥ 4 toxicity, both by CTCAE v4.03 criteria.

In addition, the following criteria and exceptions apply:

- ANC $< 500/\text{mm}^3$ for > 7 days despite GCSF support is a DLT.
- Platelet count $< 20,000/\text{mm}^3$ for more than 3 days that is considered drug-related is a DLT.
- For nausea, vomiting, or diarrhea, patients must have Grade 3 or 4 toxicity that persists at this level despite use of optimal symptomatic treatment (per local institutional guidelines), in order for these to be considered a DLT.
- Grade 3 thromboembolic events are not considered DLT.
- Any Grade 3 rash that resolves to Grade ≤ 2 within a 10 day period (including with symptomatic treatment) will not be considered a DLT.
- Cases involving hyperbilirubinemia that is primarily indirect, and considered not reflective of underlying liver disease (ie, resulting from transfusion of red blood cells), will not be considered a DLT.
- A DLT must be attributed to one of the two investigational drugs. A “drug-related toxicity” includes as events, any toxicity considered related, probably related, or possibly related to study drugs. Toxicities clearly not related to the drug, such as disease progression, environmental, unrelated trauma may not be considered “drug related toxicity”

- As per the Mays Cancer Center DSMP, any protocol modifications, problematic safety reports, unanticipated problems, and suspension or early termination of a trial must be reported to the DSMB #2 and all members of the research team at UT Health San Antonio and all affiliate sites. Furthermore, the PI of this study will promptly notify all study affiliates, the UT Health San Antonio IRB, the Mays Cancer Center DSMC, and the FDA via a FDA Form 3500Aa written IND safety report of any adverse events that are either serious and/or unexpected. Suspension and early termination of a trial must also be reported immediately to the Director of Quality Assurance who will promptly notify the sponsor and the UT Health San Antonio IRB.

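### The assessment calendar provides for less blood pressure and repeat EKG monitoring than Appendix I, Appendix III and section 7.1 state, and these passages need to be reconciled

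*Combined protocol and SAP*

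**What the plan says.** **Blood pressure**

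- Section 4.1: "Toxicity assessment will take place after each cycle".
- Section 6.0 places physical exam and toxicity assessment in the every-cycle column. There is no row for blood pressure or vital signs.
- Appendix I, 5.1 (the reproduced lenvatinib label): "Monitor blood pressure after 1 week, then every 2 weeks for the first 2 months", and at least monthly after that.
- Appendix III, on DLT and MTD: "DLT evaluation will occur weekly for the first cycle". It adds that every enrolled and treated patient is to be evaluated for DLT.
- Appendix IV collects a vitals form at the end of each cycle. It also collects vitals from each exam done in the 21-day DLT period, but marks the DLT-period forms as a requirement for phase I patients only. Section 11.1.2 uses that term for the safety run-in.
- Section 7.2 gives a figure for onset, "The median time to onset of new or worsening hypertension was 16 days", but sets no monitoring interval.

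**QT**

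- Footnote 10 of section 6.0 repeats the EKG each cycle for patients with heart failure, bradyarrhythmia or QT-prolonging medication.
- The eribulin nursing notes in section 7.1 end their list of patients to monitor with "drugs known to prolong the QT interval, and electrolyte abnormalities".
- Appendix I, 5.8: "Monitor electrocardiograms in patients with congenital long QT syndrome, congestive heart failure, bradyarrhythmias", followed by patients on QT-prolonging drugs.

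**The concern.** The calendar is the page a site works from, and here it is the sparsest of the sources. Section 4.2 does not help: it sends the reader to section 7.0 for the full list of assessments, and section 7.0 covers drug formulation and supply.

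Hypertension is the most frequent lenvatinib toxicity these documents report: 73% of any grade and 44% at grade 3 in Study 1. Drug-related grade 3 hypertension meets the general non-hematologic DLT definition in Appendix III. QT prolongation was reported in 9% of lenvatinib patients in Study 1, and section 7.1 asks for QT monitoring with eribulin as well. Appendix I, 5.9 also makes lenvatinib adjustment in hypocalcemia depend partly on ECG changes, yet footnote 10 schedules no EKG on account of an electrolyte abnormality.

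Safety is a secondary objective, and the first-cycle toxicity of ten patients informs the dose decision. If one site follows the calendar and another follows the appendices, recorded event rates will differ for reasons unrelated to the drugs.

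**Working it through.** **Inputs**

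- First lenvatinib dose on study day 2: "starting on day 2 of cycle 1" (section 4.2).
- Cycle length 21 days, window plus or minus 3 (section 6.0, footnote 2).
- Appendix I interval: 1 week, then every 2 weeks for 2 months.
- Median onset of hypertension 16 days (section 7.2 and Appendix I, 5.1, which agree). This comes from another trial and cannot be recomputed here.
- Assumption: the once-per-cycle exam falls on day 1 of the cycle and includes blood pressure. The calendar says only that it is done every cycle.

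**Blood pressure readings in the first two months**

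With cycle length L, calendar readings fall on study day 1 + L·k (k = 1, 2, …). Appendix I readings fall on day 2 + 7 + 14·k (k = 0, 1, …). Two months is taken as 56 to 61 days after the first dose, that is up to study day 58 to 63.

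| Source | Study days | Readings |
|---|---|---|
| Section 6.0, L = 21 | 22, 43 | 2 |
| Section 6.0, L = 18 in every cycle | 19, 37, 55 | 3 |
| Section 6.0, L = 24 in every cycle | 25, 49 | 2 |
| Appendix I, 5.1 | 9, 23, 37, 51 | 4 |
| Appendix III weekly evaluation, cycle 1 only | about 8, 15, 22 | 3, if blood pressure is included |

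At the nominal cycle length the calendar gives 2 readings against 4.

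**Where the difference bites**

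- Median onset: 2 + 16 = day 18, or day 17 if the first dose counts as day 1.
- The next reading after that is day 22 on the calendar (range 19 to 25) and day 23 under Appendix I. The median case is therefore picked up at about the same time on either schedule.
- Onset before day 9 would be read on day 9 under Appendix I and on day 22 on the calendar, 22 − 9 = 13 days later.
- Onset between days 23 and 37 would be read on day 37 against day 43, 6 days later.
- The documents give no onset distribution, so the number of patients in these intervals cannot be stated.

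**Repeat EKG groups**

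| Group | Footnote 10 | Section 7.1 | Appendix I, 5.8 |
|---|---|---|---|
| Heart failure | yes | yes | yes |
| Bradyarrhythmia | yes | yes | yes |
| QT-prolonging drugs | yes | yes | yes |
| Electrolyte abnormalities | no | yes | no |
| Congenital long QT syndrome | no | no | yes |

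Three groups stand in footnote 10 and five across the two other sources, so two are absent from the calendar.

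Exclusion 13 (section 3.1) removes neither group entirely. It bars a QTc above 480 ms when electrolytes are normal, so congenital long QT with a QTc at or below 480 ms can enter, and electrolyte abnormalities can arise on treatment.

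For scale only: Study 1 reported grade 3–4 hypocalcemia in 9% and hypokalemia in 6%. If those rates carried over, 0.09 × 30 = 2.7 and 0.06 × 30 = 1.8 of the 30 phase II patients. The two may overlap, and section 7.1 names no grade.

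**The case against.** Much of the case on the other side stands.

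- **Earlier evaluations exist.** A reader might infer that hypertension typically begins before the first scheduled on-treatment reading, because day 17–18 precedes day 22. That is true of the calendar taken alone. Appendix III, however, calls for evaluation at about days 8 and 15 in any treated patient; if blood pressure is taken then, the inference fails. The gap is not closed, though. Appendix III does not name blood pressure, the calendar shows no day 15 contact, and Appendix IV's vitals form records exams that were done without scheduling any.
- **Blood pressure is probably part of the exam.** Section 11.1.2 lists it among the vital signs submitted with the run-in registration exam. The missing row is thus an omission from the calendar, not proof that no reading is taken.
- **No count of late-detected cases follows.** Halving the expected hypertension cases at the median would suggest a number missed, but onsets between about days 9 and 22 are found no earlier under Appendix I at the nominal cycle length.
- **Section 4.3 is not blocked in cycle 1.** Its dose table is limited to the post-DLT period in phase II patients, so a first reading on day 22 does not disable the hypertension row in that cycle.
- **QT is not ignored.** Section 7.1 already tells staff to monitor QT in patients with electrolyte abnormalities, and section 4.3 asks for electrolytes to be monitored and corrected in everyone. It would be wrong to say these patients get no EKG or that the QTc row could never be triggered. What fails is that footnote 10 does not carry the instruction.
- **Appendix I is a label** for 24 mg single-agent use in thyroid cancer. Whether it binds trial visits is a matter of interpretation, but the protocol reproduces it without saying which parts apply.

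**Conclusion.** The concern holds as a contradiction within the protocol. For blood pressure, section 4.1 and the section 6.0 calendar conflict with Appendix I and with Appendix III; section 7.2 is not part of the conflict. At 21-day cycles the calendar gives about 2 readings in two months against 4 in Appendix I (3 against 4 if every cycle is shortened to 18 days). It lacks the 1-week reading and the 2-week spacing. Whether the weekly cycle 1 evaluation covers phase II patients is unclear, since Appendix III and Appendix IV point in different directions. For EKG, footnote 10 carries three of the five groups named elsewhere.

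The likely effect is uneven capture of hypertension and QTc events between sites. The documents do not support a figure for missed or delayed cases.

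The reading counts assume exams on day 1 of each cycle. The Study 1 rates and the 16-day median come from 24 mg monotherapy in another cancer, whereas this trial gives 20 mg with eribulin, so carrying them over is an assumption. The primary response rule is not touched.

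**What to change.** 1. Reconcile section 4.1, the section 6.0 calendar, Appendix I, Appendix III and Appendix IV on the timing of blood pressure, and show the result as its own calendar row.
2. State whether the weekly DLT evaluation applies to phase II patients and whether it includes blood pressure. Enter it in the calendar and align the Appendix IV forms with it.
3. Reconcile footnote 10 with section 7.1 and Appendix I, 5.8, so that one list of repeat-EKG groups applies throughout.
4. Correct the reference in section 4.2 that points to section 7.0 for the list of assessments.

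Which schedule and which EKG groups apply is the sponsor's clinical decision, and none is proposed here. Clinic visits on days 1 and 8 already exist and could carry readings, but their spacing is not fixed. Day 8 to the next day 1 is 22 − 8 = 14 days nominally and 14 + 3 = 17 days at the edge of the window. The interval between visits is longer still if the day 8 visit does not take place.

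The cost is a calendar edit, matching text in the appendices, and possibly a few more recorded readings or EKGs.
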